#### CONTRAINDICATIONS

19. Patient has a history of sensitivity to any of the study medications, medications used in the study (including anesthesia), or their components or a history of drug or other allergy that, in the opinion of the investigator or Medical Monitor, contraindicates their participation
20. Patient has any medical condition that may put them at increased risk with exposure to GSK1358820 including diagnosed myasthenia gravis, Eaton-Lambert syndrome, or amyotrophic

lateral sclerosis
21. Females who are pregnant, nursing or planning a pregnancy during the study

DIAGNOSTIC ASSESSMENTS AND OTHER CRITERIA
22. Patient has a PVR urine volume of >100 mL f at screening phase
23. Patient has had urinary retention or an elevated PVR urine volume g within 6 months of screening that has been treated with an intervention (such as catheterization)
24. Patient has a 24-hour total volume of urine voided >3000 mL of urine collected over 24 consecutive hours during the 3-day bladder diary collection period in the Screening phase
25. Patient is currently participating in or has previously participated in another therapeutic study within 30 days prior to the start of the Screening phase
26. Patient has any condition or situation which, in the investigator's (or subinvestigator's) opinion, puts the patient at significant risk, may confound the study results, or may interfere significantly with the patient's participation in the study

f: The PVR measurement can be repeated once; the patient is to be excluded if the repeated measure is above 100 mL

g: Voiding difficulties as a result of surgical procedures that resolved within 24 hours are not exclusionary

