### 5.3. Re-treatment Criteria

Patients can be considered for re-treatment beginning at the week 12 visit following the initial treatment or the week 12 visit following any re-treatment. The following re-treatment criteria must be used for the qualification of patient.

Qualification for re-treatment criteria:

- 1) Patient must have initiated request for re-treatment
- 2) Patient experienced  $\geq 2$  episodes of urinary urgency incontinence, with no more than one urgency incontinence-free day, as determined by the 3-day patient bladder diary completed in the week prior to the Qualification for Treatment visit
- 3) PVR urine volume must have been < 200 mL
- 4) Investigator deemed re-treatment appropriate and no condition or situation existed which, in the investigator's opinion (or sub-investigator's opinion), put the patient at significant risk from receiving a repeat treatment

Once these criteria are met, the patient who qualifies should be treated within 21 days of qualification, provided that all the following re-treatment criteria are met on the day of re-treatment.

Day of re-treatment criteria:

- 1) Central laboratory urine analysis for possible UTI using the sample collected at qualification for re-treatment visit had been reviewed by investigator (or sub-investigator)
- 2) Negative urine dipstick reagent strip test (for nitrites and leukocyte esterase)
- 3) Patient was asymptomatic for a UTI, in the opinion of the investigator (or sub-investigator)

- 4) Patient had discontinued any antiplatelet or anticoagulant therapy or medications with anticoagulative effects 3 days prior to re-treatment. Some medications may need to have been withheld for > 3 days per clinical judgment of the investigator (or sub-investigator)
- 5) Negative urine pregnancy test for women of childbearing potential.
- 6) Patient had initiated appropriate antibiotic medication 1 to 3 days prior to re-treatment
- 7) No occurrence of bladder stones since entry into the study
- 8) A minimum of 12 weeks (84 days) must have elapsed since the previous treatment
- 9) Period after 1st treatment did not exceed 36 weeks
- 10) Investigator (or sub-investigator) continued to deem a repeat treatment was appropriate and no condition or situation existed which in the investigator's opinion put the patient at significant risk from receiving a repeat treatment

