5.2. Baseline Definitions

For all endpoints (except as noted in baseline definitions) the baseline value will be the latest pre-dose assessment with a non-missing value, including those from unscheduled visits. For urinary diary data, the baseline value will be the latest pre-dose 3-day diary which has at least one valid diary day. If time is not collected, Day 1 assessments are assumed to be taken prior to first dose and used as baseline. This baseline means “study baseline”. “Study baseline” will be used for all analyses using baseline data (e.g., change from baseline).

Unless otherwise stated, if baseline data is missing no derivation will be performed and baseline will be set to missing.

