8. SAFETY ANALYSES

The safety analyses will be based on the “Safety” population, unless otherwise specified. In detail, each Safety population will be used for each study phase as below table. In principle, summaries for TC1 will be only by treatment group, and summaries for GTC1, GTC2, GTC3 and Overall will be by treatment group and its total.

For AEs:

Study phase	Population	Summary Group
TC1	SPDB	By treatment group
GTC1	SP1	By treatment group and total
GTC2	SP2	By treatment group and total
GTC3	SP3	By treatment group and total
Overall	SP1	By treatment group and total

NOTES:

- The definition of population is described in [Analysis Populations](#).

For other than AEs:

Study phase	Population	Summary Group
TC1	SPDB	By treatment group
GTC1, GTC2, GTC3	SP1	By treatment group and total

NOTES:

- The definition of population is described in [Analysis Populations](#).

Safety data from unscheduled visit will not be included in safety analysis (but included in listing), and safety data at last visit will be treated as Study Exit in safety analyses (but treated as Withdrawal in listing).

Visit displayed in safety analyses will be summarized below table for study phases and endpoints. SPDB (for TC1) and SP1 (for GTC1, GTC2 and GTC3) will be used for these summaries. Separate displays will be provided for TC1 and for GTCs (GTC1, GTC2 and GTC3).

Endpoints	Study phase	Study visit displayed in safety analyses table
Vital Sign	TC1	Baseline, Week 2, Week 6, Week 12, Week 18, Week 24, Week 30, Week 36, Week42, Study exit
	GTC1	Study baseline, Qualification for GTC1 [1], Week 0 [1], Week 2, Week 6, Week 12, Week 18, Week 24, Week 30, Week 36, Week42, Study exit
	GTC2	Qualification for GTC2, Week 0, Week 2, Week 6, Week 12, Week 18, Week 24, Week 30, Study exit
	GTC3	Qualification for GTC3, Week 0, Week 2, Week 6, Week 12, Week 18, Study exit
Clinical laboratory (chemistry and hematology), ECG	TC1	Baseline, Week 12, Study exit
	GTC1	Study baseline, Qualification for GTC1 [1], Week 12, Study exit

CONFIDENTIAL

204947

Endpoints	Study phase	Study visit displayed in safety analyses table
	GTC2	Qualification for GTC2, Week 12, Study exit
	GTC3	Qualification for GTC3, Week 12, Study exit
Body Weight	TC1	Baseline, Study exit
	GTC1	Study baseline, Qualification for GTC1 [1], Study exit
	GTC2	Qualification for GTC2, Study exit
	GTC3	Qualification for GTC3, Study exit
PVR	TC1	Baseline, Week 2, Week 6, Week 12, Week 18, Week 24, Week 30, Week 36, Week42, Study exit

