	GTC1	Study baseline, Qualification for GTC1 [1], Week 2, Week 6, Week 12, Week 18, Week 24, Week 30, Week 36, Week42, Study exit
	GTC2	Qualification for GTC2, Week 2, Week 6, Week 12, Week 18, Week 24, Week 30, Study exit
	GTC3	Qualification for GTC3, Week 2, Week 6, Week 12, Week 18, Study exit

NOTES:

- Baseline means study baseline defined as [5.2](#).
- Study baseline will be used for the derivation of change from baseline
- Urinalysis results will be displayed by using worst case results post-baseline relative to baseline for protein and occult blood urinalysis only in accordance with IDSL standards rationale, not by visit
- Study exit includes withdrawal.
- [1]: only for subjects with Placebo at TC 1

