11.4.1.2. Study Phases for AE Data and Safety Date except for AE

Treatment State	Definition
Pre-Treatment	AE Start Date $<$ 1st treatment Date
On-Treatment	If AE onset date is on or after treatment start date & on or before treatment stop date. 1st treatment Date \leq AE Start Date \leq Study Treatment Stop Date
Onset Time Since 1st Dose (Days)	If 1st treatment Date $>$ AE Onset Date = AE Onset Date - 1st treatment Date If 1st treatment Date \leq AE Onset Date = AE Onset Date - 1st treatment Date +1 Missing otherwise.
Duration (Days)	AE Resolution Date - AE Onset Date + 1
Treatment Cycle 1 (TC1) \leq 84 days from 1st treatment	1st treatment Date \leq AE Start Date \leq 1st treatment Date +83
Treatment Cycle 1 (TC1)	1st treatment Date \leq AE Start Date (if the subject completes / withdraws without 2nd treatment) \leq Study Exit/Withdraw Date

CONFIDENTIAL

204947

Treatment State	Definition
	or (if the subject take 2nd treatment) < 2nd treatment Date
GSK1358820 Treatment Cycle 1 (GTC1)	For subjects who received GSK1358820 as 1st treatment: 1st treatment Date ≤ AE Start Date (if the subject completes / withdraws without 2nd treatment) ≤ Study Exit/Withdraw Date or (if the subject take 2nd treatment) < 2nd treatment Date For subjects who received placebo as 1st treatment: 2nd treatment Date /Time ≤ AE Start Date / Time (if the subject completes / withdraws without 3rd treatment) ≤ Study Exit/Withdraw Date or (if the subject take 3rd treatment) < 3rd treatment Date
GSK1358820 Treatment Cycle 2 (GTC2)	For subjects who received GSK1358820 as 1st treatment: 2nd treatment Date /Time ≤ AE Start Date / Time (if the subject completes / withdraws without 3rd treatment) ≤ Study Exit/Withdraw Date or (if the subject take 3rd treatment) < 3rd treatment Date For subjects who received placebo as 1st treatment: 3rd treatment Date / Time ≤ AE Start Date / Time ≤ Study Exit/Withdraw Date
GSK1358820 Treatment Cycle 3 (GTC3)	For subjects who received GSK1358820 as 1st treatment: 3rd treatment Date / Time ≤ AE Start Date / Time ≤ Study Exit/Withdraw Date For subjects who received placebo as 1st treatment: Not applicable because 3 rd treatment of GSK1358820 is not allowed for subjects who received placebo as 1st treatment
Overall	For subjects who received GSK1358820 as 1st treatment 1st treatment Date ≤ AE Start Date ≤ Study Exit/Withdraw Date For subjects who received placebo as 1st treatment 2nd treatment Date ≤ AE Start Date ≤ Study Exit/Withdraw Date

NOTES:

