- If the study withdraw date is missing then the AE will be considered to be On-Treatment.
- AE start time needs to be considered if AE start date is equal to the re-treatment date
- As for safety date except for AE (i.e., laboratory data etc.), "AE Start Date" will be replaced with the date of measurement, unless otherwise specified.

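### For placebo-first subjects, the GSK1358820-cycle laboratory, vital-sign and urinalysis tables use a baseline from before the placebo injection, so a persistent abnormality that arose on placebo counts as a shift on drug

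*SAP*

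**What the plan says.** SAP 5.2 defines a single study baseline, the latest non-missing value before the first dose. Where no time is recorded, "Day 1 assessments are assumed to be taken prior to first dose and used as baseline". The same section says that this baseline "will be used for all analyses using baseline data (e.g., change from baseline" and makes no exception for later cycles. The notes to the visit table in SAP section 8 repeat the rule for safety: "Study baseline will be used for the derivation of change from baseline". Both versions of the SAP carry this text.

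SAP 11.4.1.2 defines the GSK1358820 cycles. For subjects who received placebo first, GTC1 begins at the second treatment ("2nd treatment Date /Time ≤ AE Start Date / Time"). For laboratory and other non-AE safety data the AE start date "will be replaced with the date of measurement, unless otherwise specified", so the same boundaries apply. Protocol 5.3 sets the earliest re-treatment ("A minimum of 12 weeks (84 days) must have elapsed since the previous treatment") and closes re-treatment at 36 weeks after the first injection.

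For laboratory tests and ECG, SAP section 8 lists the GTC1 display rows as "Study baseline, Qualification for GTC1 [1], Week 12, Study exit". Footnote [1] limits the Qualification row to placebo-first subjects. Vital signs also have a Week 0 row. GTC summaries are given by treatment group and in total.

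**The concern.** The GTC tables have no concurrent control, so the reference value is the only comparator a reader has. For GSK-first subjects, study baseline is the last state before drug. For placebo-first subjects it is the state before a placebo injection and at least 12 weeks of follow-up.

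A laboratory value, vital sign or urinalysis category that changed during those weeks and did not return is therefore tabulated as a change in a GSK1358820 cycle. The total column then pools change since before drug with change since before placebo.

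The SAP already re-anchors adverse events and duration of follow-up at the first GSK1358820 dose for these subjects (11.4.1.2 and 11.6.2). It does not do so for measured safety data.

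**Working it through.** **1. The interval.** Protocol 5.3 gives 12 weeks as 84 days, and 12 × 7 = 84 reproduces it. The upper limit is 36 × 7 = 252 days. Protocol Table 1 places the pre-treatment chemistry and haematology sample at screening, up to 28 days before the first injection, so that baseline can lie up to 252 + 28 = 280 days before the first GSK1358820 dose. For placebo-first subjects GTC2 starts at the third treatment, at least 2 × 84 = 168 days after placebo. GTC3 does not apply to them.

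**2. Which tables depend on the reference.**
- Chemistry and haematology change: 3.104 and 3.110.
- Chemistry and haematology normal-range shift: 3.106 and 3.112.
- Vital-sign change: 3.121.
- Worst-case protein and occult blood: 3.114. SAP 8.3 compares the baseline category with the worst later category.

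ECG findings are tabulated by visit without a shift. AEs are assigned by onset date and use no baseline.

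**3. Effect on a shift table.** Take placebo-first subjects who are normal at study baseline. Let q be the share who become abnormal on placebo and stay so. Let e be the share of the rest who become abnormal after GSK1358820.
- From study baseline, the GTC1 normal-to-abnormal share is q + (1 − q)e.
- From a pre-GSK1358820 reference, it is (1 − q)e.
- The difference is exactly q.

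The documents give neither rate, so a range is shown:

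| q | e | study baseline | pre-GSK1358820 reference |
|---|---|---|---|
| 0 | 2% | 2.0% | 2.0% |
| 2% | 2% | 4.0% | 2.0% |
| 5% | 2% | 6.9% | 1.9% |
| 10% | 2% | 11.8% | 1.8% |
| 2% | 5% | 6.9% | 4.9% |
| 5% | 5% | 9.8% | 4.8% |
| 10% | 5% | 14.5% | 4.5% |

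For means, the change shown after GSK1358820 equals the drift on placebo plus the change after drug.

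**4. Counts and the total.** Assume that 90 of the 120 planned placebo subjects cross over, that all 120 GSK-first subjects contribute, and that all are normal at study baseline. Misattributed shifts per test are 90 × 2% = 1.8, 90 × 5% = 4.5 or 90 × 10% = 9. In the total column, 90 + 120 = 210, so the excess is 1.8/210 = 0.9, 4.5/210 = 2.1 or 9/210 = 4.3 percentage points.

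**5. PVR, checked separately.** A no-effect simulation (2 million subjects per setting) assumed lognormal PVR with median 20–40 mL, total log-SD 1.0 and within-subject log-SD 0.5–0.7. It applied the 100 mL entry limit with one repeat and the re-treatment limit of less than 200 mL. The distribution values are not in the documents. The spurious mean change was:
- placebo-first, from study baseline: +3.1 to +16.6 mL;
- GSK-first, from study baseline: +3.4 to +18.5 mL;
- placebo-first, from the qualification value: +0.7 to +6.9 mL.

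**The case against.** The strongest reply is that the drift is displayed, not hidden. The by-visit GTC1 tables give placebo-first subjects a Qualification row, and a Week 0 row for vital signs. Laboratory shifts are also by visit, so an abnormality present before drug appears in the Qualification counts. These subjects have their own column. The TC1 tables report the placebo period separately (for example 3.103, 3.105 and 3.120), and the raw-value GTC tables need no baseline. Clinically significant laboratory abnormalities are AEs under Protocol 12.3.1 and are placed by onset date. The GTC tables are descriptive. A single fixed baseline is also a recognised convention that keeps change comparable across cycles.

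Most of this stands. A reader might infer that all placebo-period change is passed off as drug effect with no trace. The documents do not support that, because group-level drift can be read from the GTC1 by-visit tables.

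Four gaps remain:
- Rows give group counts, not each subject's path from Qualification to later visits.
- The total still mixes two references.
- GTC2 shows no row from before the first GSK1358820 dose; its Qualification row follows that dose.
- Worst-case urinalysis has no visit rows at all.

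The laboratory listing of subjects with out-of-range values lets someone trace individual cases, but that does not correct the summary tables.

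**Conclusion.** The point holds for the GTC laboratory change and shift tables, vital-sign change and worst-case urinalysis. The rule is explicit, and no pre-GSK1358820 reference is defined for placebo-first subjects. The shift share in their column is overstated by q, the persistent new abnormality on placebo. That is 2 to 10 percentage points over the assumed range and nothing if q is zero. The crossover number of 90 is also an assumption.

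Three stronger readings are tempting but not supported.
- A reader might infer that PVR has the worst problem, because entry is capped ("Patient has a PVR urine volume of >100 mL" is an exclusion) and later values will drift upwards. The cap applies to everyone randomised, and under the assumed model the artefact is nearly equal in the two groups (+3.1 and +3.4 mL at the low end, +16.6 and +18.5 mL at the high end). Re-anchoring only placebo-first subjects would pull them apart (+0.7 and +3.4 mL; +6.9 and +18.5 mL) and make the PVR total less coherent.
- A reader might infer that the repeat-dose safety evidence rests on GTC1. GTC1 is the first GSK1358820 cycle; repeat dosing is covered by GTC2 and GTC3.
- A reader might infer that the main conclusions are at risk. AE tables, the randomised TC1 comparison and the efficacy tests do not use this reference in the GSK1358820 cycles.

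**What to change.** Add one rule to SAP section 8. In the GTC laboratory change and shift tables, vital-sign change table and worst-case urinalysis table, the reference for placebo-first subjects is the last non-missing value before the first GSK1358820 dose (Qualification or Week 0). For GSK-first subjects it remains study baseline. Keep the study-baseline version as a supplement, and keep study baseline for TC1 and efficacy.

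Leave the PVR tables (3.125, 3.145) on study baseline. Alternatively, show a pre-GSK1358820 reference in the Placebo/GSK1358820 column only and not in the total.

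The cost is one sentence, one derived variable, some extra displays and a footnote explaining the two references. No new data are needed: Protocol Table 2 already schedules these assessments at qualification, within 21 days before re-treatment. The affected tables are produced only at the final analysis, so the interim outputs do not change.

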8.1. Adverse Events Analyses

Adverse events analyses including the analysis of adverse events (AEs), Serious (SAEs) and other significant AEs will be based on GSK Core Data Standards. The details of the planned displays are provided in [Appendix 10: List of Data Displays](#).

All AEs will be classified using the standard GSK Medical Dictionary for Regulatory Activities (MedDRA) dictionary, and grouped by SOC and PT, unless otherwise stated. The investigator will evaluate all AEs with respect to seriousness, severity, and causality.

AEs analyses will be by treatment group (and total for GTC1, GTC2, GTC3 and Overall) and study phases (i.e., TC1, TC1 <= 84 days, GTC1, GTC2, GTC3 and Overall, see section [11.4](#)). Note that Overall includes all AEs after GSK1358820 treatment.

The number and percentage of subjects experiencing an AE and the total number of AEs (the number of subjects with any AEs) will be summarized for each of the following AE categories by treatment group (and total for GTC1, GTC2, GTC3 and Overall):

- All AEs (by SOC and PT; by SOC and PT and maximum severity)
- Common AEs (by PT)
- Serious AEs (by SOC and PT)

CONFIDENTIAL

204947

- Treatment related AEs (by SOC and PT; by SOC and PT and maximum severity)
- Study drug related AEs (by SOC and PT; by SOC and PT and maximum severity)
- Injection related AEs (by SOC and PT; by SOC and PT and maximum severity)
- Fatal serious AEs (by SOC and PT)
- AEs resulting in withdrawal from study (by SOC and PT)
- Serious treatment related AEs (by PT, for PLS)
- Non-serious treatment related AEs (by PT, for PLS)

The tabular summary for each category of AE listed above will include the number of subjects who reported at least one event, and percentage of subjects who reported at least one AE (incidence) by treatment group (and total for GTC1, GTC2, GTC3 and Overall) for each SOC (where applicable), each PT, and overall. By default, adverse events will be sorted by MedDRA SOCs, in descending order from the SOC with the highest total incidence (i.e., summed across all treatment groups) for any adverse event within the class, to the SOC with the lowest total incidence. If the total incidence for any two or more adverse events is equal, the events will be presented in alphabetical order. Only SOCs with observed AE PTs will be presented. Repeat sort order for MedDRA PTs within each SOC.

Common AEs will be defined as $\geq 5\%$ in overall frequency.

The table for All AEs by SOC and PT in TC1 will be repeated for age, sex, BPH (only for male) and diabetes subgroups. See section [5.4.2](#) for details on the subgroup categories.

As for AEs by SOC and PT and severity, the number and percentage of subjects will be summarized as mild, moderate and severe on the maximum severity observed within each PT for a given subject.

As for requirement by FDAAA and EudraCT, the number and percentage of subjects and the number of events will be summarized for common ($\geq 5\%$) non-serious AEs by SOC and PT in TC1, GTC1, GTC2 and GTC3.

Listing will be produced for each of the following AE categories:

- All AEs
- Serious AEs
- AEs resulting in withdrawal from study (by SOC and PT)

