Urinary retention	
As the result of integrated data with 1 completed phase 2 study (191622-077), 2 completed pivotal phase3 study (191622-095 and 191622-520) and an interim cut of the long-term extension study (191622-096), the frequency of urinary retention as an adverse event occurred in 7.1% of patients in the 100 U BOTOX group and 0.5% of patients in the placebo group (refer to IB section 5.2.4.2 Overactive Bladder).
 
Intradetrusor injection of BOTOX causes a detrusor muscle relaxation that leads to a decrease in the contractions of the detrusor muscle. This detrusor muscle relaxation may lead to an inability of the detrusor muscle to effectively contract during voiding in some patients thus causing a residual accumulation of urine in the bladder evident as an increased PVR volume, or may manifest as a patient's inability to void due to urinary retention (refer to IB section 5.2.5 Clinical Safety in the published literature ).
	
Patients with potential risk for these events will be excluded from this study (refer to Protocol section 5.2 exclusion criteria 22, 23 and 26 )
 
PVR urine volume will be assessed at each visit. Clean intermittent catheterization (CIC) and additional follow-up visit will be performed dependent on the PVR as well as subject's symptoms (refer to Protocol section 7.4.7.Post-void residual urine volume and Appendix 5 Management guideline of PVR).

Pyelonephritis	
In OAB clinical studies, pyelonephritis as an AE was also very uncommon and was reported as a non-serious adverse event in one patient during placebo-controlled treatment cycle 1. However, based on the patient population who will be receiving instrumentation to deliver intradetrusor injections of BOTOX, and a potential temporary increase in PVR urine post treatment, mainly in
	
Please refer to the mitigation strategy UTIs.

	the first 12 weeks, patients with bladder disorders with urinary incontinence who have a prior UTI may potentially progress from UTI to pyelonephritis.	
Other		

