1.1. RAP Amendments

Revision chronology:

RAP Section	Amendment Details
Reporting and Analysis Plan_Study204947_Final_V1 [16-APR-2018]	
Reporting and Analysis Plan_Study204947_Amendment_Final_V1 [05-JUL-2018]	
4.1	
 Updated PDMP version
5.4.1	
 Added the wording “, and the derived values based on 11.6.3 will be used for analysis purpose” for clarification.
6.1.3	
 Corrected from “2 categories: Frequencies of None or “Mild, Moderate or Severe”” to “2 categories: Frequencies of “None or Mild”, “Moderate or Severe”” for correction of errors.
8.1	
 Corrected from “Common AEs will be defined as $\geq 5\%$ incidence in any treatment group (and total for GTC1, GTC2, GTC3 and Overall)” to “Common AEs will be defined as $\geq 5\%$ in overall frequency.” to align with GSK IDSL standards.

CONFIDENTIAL

204947

8.2	
 Deleted following sentence ". In order to confirm that AEs of special interest have not occurred, all the name of AEs of special interest will be displayed in summary table (i.e., the event which have not occurred in any treatment group will be displayed as 0 for number of events in both treatment groups)." to align with actual display.
8.6	
 Added section of patient profile listings for GSK requirement.
11.10	
 Updated Table of contents for correction of errors and requested listings.
11.12	
 Added the summary of information about CIC to use for tables/listings for further explanation.
11.13	
 Added how to identify the records for the interim analysis for clarification of data cut-off rule.

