11.5.2. Reporting Standards

General	

 The current GSK Integrated Data Standards Library (IDSL) will be applied for reporting, unless otherwise stated (IDSL Standards Location: https://spope.gsk.com/sites/IDSLLibrary/SitePages/Home.aspx): 
 4.03 to 4.23: General Principles 5.01 to 5.08: Principles Related to Data Listings 6.01 to 6.11: Principles Related to Summary Tables 7.01 to 7.13: Principles Related to Graphics Do not include subject level listings in the main body of the GSK Clinical Study Report. All subject level listings should be located in the modular appendices as ICH or non-ICH listings 	
Formats	

 GSK IDSL Statistical Principles (5.03 & 6.06.3) for decimal places (DP's) will be adopted for reporting of data based on the raw data collected, unless otherwise stated. Numeric data will be reported at the precision collected on the eCRF. The reported precision from non eCRF sources will follow the IDSL statistical principles but may be adjusted to a clinically interpretable number of DP's. 	
Planned and Actual Time	

 Reporting for tables, figures and formal statistical analyses: 
 Planned time relative to dosing will be used in figures, summaries, statistical analyses and calculation of any derived parameters, unless otherwise stated. The impact of any major deviation from the planned assessment times and/or scheduled visit days on the analyses and interpretation of the results will be assessed as appropriate. Reporting for Data Listings: 
 Planned and actual time relative to study drug dosing will be shown in listings (Refer to IDSL Statistical Principle 5.05.1). Unscheduled or unplanned readings will be presented within the subject's listings. 	
Unscheduled Visits	

 Unscheduled visits will not be included in summary tables and/or figures. All unscheduled visits will be included in listings. 	

CONFIDENTIAL

204947

Descriptive Summary Statistics	
Continuous Data	Refer to IDSL Statistical Principle 6.06.1 N, mean, standard deviation (or standard error), median, minimum and maximum.
Categorical Data	N, n, frequency, %
Graphical Displays	
• Refer to IDSL Statistical Principals 7.01 to 7.13.	

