3.87.	SP1	AE1	Summary of Fatal Serious Adverse Events: Overall Period	GSK CTR	Y	Y
3.88.	SP1	AE1	Summary of Serious Adverse Events: Overall Period	IDSL / GSK CTR	Y	Y
3.89.	SP1	AE3	Summary of Adverse Events Leading to Withdrawal from Study / Permanent Discontinuation of Study Treatment by Overall Frequency: Overall Period	IDSL	Y	Y
3.90.	SP1	AE1	Summary of Special Interest Adverse Events: Overall Period		Y	Y
AEs for PLS						
3.91.	SPDB	AE3	Summary of Serious Treatment Related Adverse Events by Overall Frequency: TC1	PLS		Y
3.92.	SP1	AE3	Summary of Serious Treatment Related Adverse Events by Overall Frequency: GTC1	PLS		Y
3.93.	SP2	AE3	Summary of Serious Treatment Related Adverse Events by Overall Frequency: GTC2	PLS		Y
3.94.	SP3	AE3	Summary of Serious Treatment Related Adverse Events by Overall Frequency: GTC3	PLS		Y

CONFIDENTIAL

204947

Safety : Tables						
No.	Population	IDSL / TST ID / Example Shell	Title	Programming Notes	Report at Interim	Report at Final
3.95.	SP1	AE3	Summary of Serious Treatment Related Adverse Events by Overall Frequency: Overall Period	PLS		Y
3.96.	SPDB	AE3	Summary of Non-Serious Treatment Related Adverse Events by Overall Frequency: TC1	PLS		Y
3.97.	SP1	AE3	Summary of Non-Serious Treatment Related Adverse Events by Overall Frequency: GTC1	PLS		Y
3.98.	SP2	AE3	Summary of Non-Serious Treatment Related Adverse Events by Overall Frequency: GTC2	PLS		Y
3.99.	SP3	AE3	Summary of Non-Serious Treatment Related Adverse Events by Overall Frequency: GTC3	PLS		Y
3.100.	SP1	AE3	Summary of Non-Serious Treatment Related Adverse Events by Overall Frequency: Overall Period	PLS		Y
Laboratory: Chemistry						
3.101.	SPDB	LB1	Summary of Chemistry Data: TC1		Y	Y
3.102.	SP1	LB1	Summary of Chemistry Data: GTCs			Y
3.103.	SPDB	LB1	Summary of Chemistry Changes from Baseline: TC1	ICH E3	Y	Y
3.104.	SP1	LB1	Summary of Chemistry Changes from Baseline: GTCs	ICH E3		Y
3.105.	SPDB	LB3	Summary of Shift from Baseline with Relative to Normal Range in Chemistry Results: TC1	ICH E3	Y	Y
3.106.	SP1	LB3	Summary of Shift from Baseline with Relative to Normal Range in Chemistry Results: GTCs	ICH E3		Y
Laboratory: Hematology						
3.107.	SPDB	LB1	Summary of Hematology Data: TC1		Y	Y

CONFIDENTIAL

204947

Safety : Tables						
No.	Population	IDSL / TST ID / Example Shell	Title	Programming Notes	Report at Interim	Report at Final
3.108.	SP1	LB1	Summary of Hematology Data: GTCs			Y
3.109.	SPDB	LB1	Summary of Hematology Changes From Baseline: TC1	ICH E3.	Y	Y

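### Does the 5% overall-frequency cut for common adverse events hide drug-related events in the double-blind tables?

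*SAP*

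**What the plan says.** The rule is in SAP 8.1: "Common AEs will be defined as $\geq 5\%$ in overall frequency". In TC1 it governs Table 3.2 (the first 84 days) and Table 3.15 (the whole cycle). Both use the double-blind safety population, which holds both randomized arms, and both carry overall frequency in their titles.

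The SAP text does not define overall frequency. Four other places bear on it:

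- The sort rule in SAP 8.1 starts from "the SOC with the highest total incidence (i.e., summed across all treatment groups".
- SAP 8 says of the columns: "In principle, summaries for TC1 will be only by treatment group". TC1 tables therefore need not show a pooled percentage.
- SAP 1.1 gives the reason for the present wording, "to align with GSK IDSL standards". SAP 11.5.2 says that this standard "will be applied for reporting, unless otherwise stated".
- SAP 8.1 has a separate disclosure table (Table 3.23 in TC1), "summarized for common ($\geq 5\%$) non-serious AEs by SOC and PT in TC1, GTC1, GTC2 and GTC3". It does not say whether that 5% is per arm or pooled.

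The display standard itself and the mock shells are separate documents and were not available.

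**The concern.** TC1 is the only randomized, placebo-controlled safety comparison in the trial. Allocation is 1:1, so a pooled percentage is roughly the average of the two arm percentages. An event that occurs only on active has its percentage halved before it meets the 5% cut, while an event equally frequent in both arms keeps its full percentage. A pooled cut therefore favours background events over events that separate the arms, which seems backwards for a comparative safety table.

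Urinary retention, a risk the protocol names in section 4.6.1, appears to show this: 7.1% on active is above 5%, but the pooled figure is below it. Someone who read only the short table could miss such an event.

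**Working it through.** **Inputs.** 120 subjects per arm (SAP 2.3). Urinary retention 7.1% and 0.5%, urinary tract infection 26.4% and 10.1%, active and placebo (Protocol 4.6.1). All other rates below are assumptions. The plan states no figure for this rule, so there is none to reproduce.

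**Thresholds.** Pooled: 0.05 × 240 = 12 subjects. Either arm: 0.05 × 120 = 6 subjects in one arm. With no placebo cases, up to 11 of 120 active subjects (9.2%) can have an event that stays off the pooled list.

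**Pooled rates.** Retention: (7.1 + 0.5)/2 = 3.8%. Urinary tract infection: (26.4 + 10.1)/2 = 18.25%.

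**Chance of being listed.** Let A and P be independent binomial counts with n = 120 each.

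- Pooled rule: Pr(A + P ≥ 12)
- Either-arm rule: 1 − Pr(A ≤ 5) × Pr(P ≤ 5)

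| Active / placebo | Pooled | Either arm |
|---|---|---|
| 6% / 0% | 6% | 73% |
| 8% / 0% | 25% | 92% |
| 10% / 0% | 54% | 98% |
| 7.1% / 0.5% (retention) | 20% | 86% |
| 26.4% / 10.1% (urinary tract infection) | >99.9% | >99.9% |
| 8% / 2% | 54% | 93% |
| 8% / 4% | 78% | 95% |
| 10% / 2% | 78% | 98% |
| 10% / 3% | 86% | 99% |
| 6% / 6% | 78% | 93% |
| 4% / 4% | 26% | 58% |
| 3% / 3% | 6% | 28% |
| 2% / 2% | 0.4% | 7% |

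For retention the result depends little on arm size. With 110, 115 or 125 per arm, the pooled rule gives 22%, 16% or 16%, and the either-arm rule 80%, 83% or 79%.

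If the rule pools, the arithmetic behind the concern is therefore right. Three checks decide whether it matters.

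**1. Does the plan say that it pools?** Not outright. The summed-across-arms wording belongs to the sort order, not to the 5% cut. In SAP 8.1, overall is also the name of a study phase and of the any-event row. Overall frequency also stands in the titles of tables with no stated 5% cut, for example Table 3.96: "Summary of Non-Serious Treatment Related Adverse Events by Overall Frequency: TC1". There it looks like an ordering label. Pooling remains the likeliest reading, because the study-phase sense cannot apply to a table with a placebo column, but the display standard would be needed to settle it.

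**2. What does a reader lose if it does pool?** These TC1 tables (SAP 11.10.8) are planned by treatment group without this cut:

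| Content | First 84 days | Whole cycle |
|---|---|---|
| All events | 3.1 | 3.10 |
| By maximum severity | 3.6 | 3.19 |
| Treatment-, drug- and procedure-related | 3.3 to 3.5 | 3.16 to 3.18 |
| Special interest | 3.66 | 3.70 |
| Non-serious, treatment-related | – | 3.96 |

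An event left off Tables 3.2 and 3.15 still appears by arm in 3.1 and 3.10. If the investigator judged it related, it also appears in the related-event tables. Retention is an event of special interest (SAP 11.6.4) and has its own analyses of duration (Table 3.141) and time to onset with a hazard ratio (Table 3.143; SAP 8.5.2 and 8.5.4). The one example with rates from the documents is thus among the most fully reported events in the plan. Those rates are not a TC1 forecast either, because the integrated data include "an interim cut of the long-term extension study (191622-096), the frequency of urinary retention as an adverse event occurred in 7.1% of patients".

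**3. Is the per-arm cut plainly better?** No. It more than doubles the chance that an event at 4% in both arms is called common (26% to 58%), and nearly quintuples it at 3% (6% to 28%). The short table would gain background rows below its own nominal threshold. The gap in favour of the per-arm cut is widest at 0% on placebo and narrows as placebo events appear: at 10% / 3% it is 86% against 99%.

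The tables for the GSK1358820 cycles and the overall period contain only events after active treatment, so no placebo experience dilutes them.

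**The case for a change.** The best case for the concern is this. The short common-event table is the one people scan first, and its row list should not lean away from events that separate the arms. At the same 6% on active, the chance of being listed falls from 78% to 6% only because placebo subjects do not have the event. The percentage that selects the rows may not even be printed in the table. A per-arm rule would take one sentence and one programming parameter, and SAP 11.5.2 allows a stated departure from the standard.

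Much of this stands as description. The tilt is real if the rule pools, and the change would be cheap. It does not follow that the plan is wrong. The summary of safety analyses in Protocol 9.4.2 asks for frequencies by system organ class and preferred term, related events, events leading to discontinuation, intensity and serious events, and all of these are planned by arm. It asks for neither a common-event table nor a per-arm threshold. The sponsor chose the cut to match its display standard, and the alternative trades one kind of imbalance for another.

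It is also true that the SAP does not define overall frequency for TC1 and does not give the basis of the 5% in Table 3.23. Both could be stated more fully, but that is missing detail in display specifications and not an analysis error.

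**Conclusion.** The concern does not hold. On the likeliest reading, the cut makes an event confined to the active arm reach 10% instead of 5% before it enters Tables 3.2 and 3.15. At the protocol's retention rates, that means a 20% instead of an 86% chance of being listed. The effect stops at row selection in those two tables. No event count, arm-specific rate, hypothesis test or safety conclusion changes, and the same events appear by arm without this cut elsewhere in the TC1 set. A per-arm cut would be an equally legitimate display convention, with more low-rate background rows.

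The figures assume 120 treated subjects per arm, independent binomial counts and pooling of both arms. The retention rates come from earlier integrated data and serve only as an illustration. The judgement that nothing is lost needs none of these assumptions; it rests on the planned table list.
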